Nudging Patients to Increase Shingles Vaccination

Statistical Analysis Plan

NCT06238726

7/9/2025

Brief Summary

The purpose of this study is to test whether messages encouraging patients to ask about a shingles vaccine at an upcoming appointment will increase shingles vaccination rates. The study will also test which of several message versions is most effective.

Detailed Description

Shingles is a painful disease caused by reactivation of the varicella zoster (chickenpox) virus. About a third of adults in the US will develop shingles in their lifetime, with the highest prevalence in adults ages 50 and older. Roughly one in ten patients with shingles develops complications that can lead to long-term pain and inflammation. A two-shot shingles vaccine series is highly effective at preventing shingles and is recommended by the CDC for all adults ages 50 and over.

The present study tests whether sending patients messages encouraging them to ask about the shingles vaccine at an upcoming primary care appointment increases vaccination rate relative to Passive Control (no messages). Additionally, four message arms vary as a function of risk (message includes or does not include a statement telling patient they are at high risk for shingles because they are age 50+) and facts (message includes or does not include several facts about shingles and the vaccine), with the no-high-risk, no-facts arm designated as the Active Control arm.

Message arms are crossed with two additional randomized variables: number of messages (2 messages or 3 messages) and cost information (the presence or absence of information about the cost of the vaccine in the final message).

Methods

Eligible patients with an upcoming shingles vaccine-eligible appointment were randomized to one of the following arms:

1. Passive control: No message
2. Active control: Messages encouraging patients to ask about the shingles vaccine at their upcoming appointment.
3. High risk: Messages informing patients that they are at high risk for shingles because they are ages 50+, and encouraging them to ask about the shingles vaccine at their upcoming appointment.
4. Multi-fact: Messages with facts about shingles and the shingles vaccine, and encouraging them to ask about the vaccine at their upcoming appointment.
5. High-risk + multi-fact: Messages informing them that they are at high risk for shingles because they are ages 50+, with additional facts about shingles and the shingles vaccine, and encouraging them to ask about the vaccine at their upcoming appointment.

Patients were additionally randomized to one of the following message **frequency** conditions:

1. Two messages: Messages 3 days and 1 day before the appointment
2. Three messages: Messages 3 days, 2 days, and 1 day before the appointment

Finally, patients were randomized to one of the following **cost** conditions:

1. Cost Omitted: the cost of the vaccine was not mentioned in the final message 1 day prior to the appointment

2. Cost Mentioned: The cost of the vaccine was mentioned in the final message 1 day prior to the appointment.
 - a. In this arm, cost messages varied by whether the patient was a Geisinger Health Plan (GHP) member in a plan that allowed them to get the vaccine at no cost (the vast majority of GHP members):
 - i. Eligible GHP members were told that they could get the vaccine at no cost
 - ii. Those without GHP (and the few GHP members for whom the vaccine was not definitively covered at no cost) were told that “most patients” could get the flu vaccine at no cost

Patients were randomized on the phone number level, so patients who shared a phone number were sent the same message version.

Power Analysis

The baseline vaccination rate is 4.1% (i.e., the rate of patients not vaccinated against shingles who get a vaccine at a given eligible appointment). With 50,000 patients, and 10,000 patients per arm, we have 80% power to detect an increase in shingles vaccination rates of 0.8 percentage points, 4.1% to 4.9%, with two-tailed alpha = .05 for any comparison between message arms.

Project Status

Enrollment surpassed 50,000 patients on 6/8/2025, and as described below, we continued enrolling non-GHP patients after reaching that target. However, Geisinger decommissioned the text messaging platform that the study was running at the end of June 2025, 15 days short of our intended non-GHP extension and we ended the trial at that time. Our last day of enrolling new patients was 6/27/2025 for appointments on 6/30/2025, and our final sample size was 50,785 patients.

We have not yet extracted outcome data as of this writing.

Past Project Status Notes

Enrollment began with patients who have a GHP membership, followed five weeks later by enrollment for those without GHP (and the few patients with GHP who did not have guaranteed vaccine coverage at no cost, who were grouped with non-GHP members for the study). Enrollment for each insurance group (GHP members, non-GHP members) began with a 2-week pilot period, with a limited number of new patients (e.g., 100 to 200) enrolled per day in that insurance group (these patients were randomly selected from the eligible patients). Patients enrolled during the pilot periods will be included in all analyses, as no changes were made to outreach prior to the full rollout.

From September through December 2024, a flu vaccination text message nudge campaign ran at Geisinger for similar appointments as this shingles vaccination study. Clinical leadership decided that patients should only receive nudge messages about one vaccine per appointment, and that flu shot messages should be prioritized during flu season. Instead of pausing shingles vaccination messages entirely during the flu campaign, the team enrolled patients in the shingles study if they had already gotten a flu vaccine this flu season according to the EHR.

The original plan was to run the study for one year for each insurance group (GHP, non-GHP), with at least 50,000 total patients expected to be enrolled. However, because of the flu shot prioritization, enrollment dropped substantially during Fall 2024 and there was less certainty that enrollment would reach 50,000 patients during the predefined time frame. Therefore, we decided to extend the study until enrollment reaches 50,000 patients. For non-GHP patients, the study will run for 5 additional weeks before stopping completely, because non-GHP launch occurred 5 weeks after GHP launch. This way, the study length will be the same for both insurance groups. However, the study may be terminated early, if 50,000 patients are not enrolled by the time the current text messaging platform is abandoned at Geisinger; this is slated to occur by early summer 2025.

Planned Analyses

Primary Outcome: Received a first shingles vaccination on the appointment date (y/n) [Time Frame: 3 days after enrollment]

We will pull vaccination data from the EHR and from GHP claims for this outcome. Because the intervention is intended to increase the likelihood of vaccination at Geisinger appointments, we expect most vaccinations will be recorded in the EHR. We will pull data from GHP claims for completeness, as it is possible that patients were motivated by our messages to get vaccinated, which they chose to do outside Geisinger, and that such vaccinations would be reflected in claims data but not in the EHR.

We will extract primary outcome data from the EHR in July 2025. Insurance claims can take up to 90 days to process, so we will extract the final shingles vaccination claims data for the primary outcome on or after September 29, 2025—90 days after the last appointments in the study, plus an additional day to account for potential data refresh delays.

If there are discrepancies between EHR and claims data regarding vaccine dates, we will use EHR data unless the EHR record is marked as "historic." In such cases, we will use the claims data.

We will run the following analyses for the primary outcome:

Question 1: Do any of the message arms increase shingles vaccination relative to passive control?

Analysis 1 (Confirmatory): We will test the hypothesis that any of the message arms significantly increases shingles vaccination relative to passive control. We will run an OLS regression including a categorical predictor variable coding for each individual arm, with passive control as the baseline.

Question 2: Does shingles vaccination differ between patients sent messages that mention the cost of the vaccine, compared with those sent messages that do not mention the cost?

Analysis 2 (Exploratory): We will run an OLS regression to test whether vaccination differs as a function of cost information (0 = cost omitted, 1 = cost mentioned). This analysis will be limited

to patients randomized to a message arm (Active control, High risk, Multi-fact, High risk + multi-fact).

Question 3: Does shingles vaccination differ between patients who were sent two pre-appointment messages about vaccination versus those sent three messages?

Analysis 3 (Exploratory): We will run an OLS regression to test whether vaccination is different as a function of the number of messages patients were sent (0 = patient was randomized to be sent two messages; 1 = patient was randomized to be sent three messages). This analysis will be limited to patients randomized to a message arm (active control, high risk, multi-fact, high risk + multi-fact).

Other Pre-specified Outcomes

We will run the analyses described above on the following additional outcomes:

1. First shingles vaccination [Time Frame: In the 10 days following enrollment]

Received a first shingles vaccination in the 10 days following enrollment (y/n)

2. Attended scheduled appointment [Time Frame: 3 days after enrollment]

Attended the target vaccine-eligible appointment (y/n)

3. First shingles vaccination [Time Frame: In the 14 months following enrollment]

Received a first shingles vaccination in the 14 months following enrollment (y/n)

4. Time to first shingles vaccination [Time Frame: In the 14 months following enrollment]

Number of days between enrollment and first shingles vaccination

5. Completion of shingles vaccine series [Time Frame: In the 14 months following enrollment]

Completed shingles vaccination series by getting a second shingles vaccination (y/n)

6. Time to completion of shingles series [Time Frame: In the 14 months following enrollment]

Number of days between first and second shingles vaccination

7. Shingles diagnosis [Time Frame: In the 14 months following enrollment]

Diagnosed with shingles (y/n)

As with the primary outcome, we will collect both EHR and claims data to support other pre-specified outcomes (vaccination and diagnosis). We will use a 91-day lag to allow sufficient time for claims to be processed.

Exploratory analysis with the primary outcome

1. Interaction between including risk and facts

The four active arms in the study are a pragmatic 2x2 design, where two arms contain risk information (high-risk, high-risk + multi-fact) and two arms include facts about the shingles vaccine (multi-fact, high-risk + multi-fact); one arm (active control) does not include either risk information or facts. We will run an OLS regression testing for an interaction between risk information and facts. The dependent variable will be the primary outcome of vaccination at the target appointment. The independent variables will be risk information (0 = no high-risk information, 1 = high risk information) and facts (0 = no facts about shingles or the vaccine, 1 = facts about shingles and the vaccine), and the interaction between risk information and facts variables. This analysis will be limited to patients who were in a message arm (active control, high risk, multi-fact, high risk + multi-fact).

2. All 2-, 3-, and 4-way interactions between risk, facts, cost, and frequency

We will run OLS regressions to explore whether any 2-, 3-, or 4-way interactions are significant between messages that include risk, facts, cost information, and message frequency. Although these analyses will be underpowered, any significant findings may inform hypotheses for future interventions. These analyses will be limited to patients who were in a message arm (active control, high risk, multi-fact, high risk + multi-fact).

3. Effects of different cost messages

Among patients assigned to get messages that mention the vaccine cost, GHP members were told they could get the vaccine at no cost. Patients who were not GHP members were told that *most* patients can get the vaccine at no cost. We will run an OLS regression to test for an interaction between cost message (cost omitted, cost mentioned) and insurance group (GHP members, non-GHP members), among patients who were in a message arm (active control, high risk, multi-fact, high risk + multi-fact).

Analysis Notes

The primary analyses described above will be intent-to-treat, but we may run follow-up robustness checks limited to patients for whom messages were delivered successfully according to messaging data.

Because patients were randomized at the phone number level, we will choose one patient per phone number to include in the primary analysis. If patients with the same phone number were enrolled on different days, we will include the first patient enrolled. If patients were enrolled on the same day, GHP members will be prioritized for inclusion. If all patients with the same phone number and appointments on the same day were in the same insurance group (GHP or non-GHP), we will randomly choose a patient to include. We may run follow-up robustness checks including all patients.

Recent work suggests that OLS regressions are appropriate in randomized experiments with binary outcome variables such as ours (Gomila, 2021).

For analyses of vaccine timing other pre-specified outcomes (time to first shingles vaccination and time to completion of shingles series), we will examine the outcome distribution before choosing an appropriate regression model (likely negative binomial or Poisson regression).

For all analyses, we will report heteroskedasticity-robust standard errors.

We plan to run exploratory analyses to understand heterogeneity in observed effects (e.g., in demographic covariates such as age, sex, race, whether the patients were GHP members).

Reference

Gomila, R. (2021). Logistic or linear? Estimating causal effects of experimental treatments on binary outcomes using regression analysis. *Journal of Experimental Psychology: General*, 150(4), 700–709. <https://doi.org/10.1037/xge0000920>

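### The confirmatory claim that any of four message arms beats one shared control has no multiplicity control; at .05 per arm, a false claim of an increase has probability 7.8%, not 2.5%

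*SAP*

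**What the plan says.** Under Planned Analyses, Analysis 1 is the only analysis labelled confirmatory. Its hypothesis is: "We will test the hypothesis that any of the message arms significantly increases shingles vaccination relative to passive control". The method follows: "We will run an OLS regression including a categorical predictor variable coding for each individual arm, with passive control as the baseline". With four message arms, that model yields four coefficients, all measured against the same control group.

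Analysis 1 gives no significance level and no rule for declaring success. The only alpha in the document is in Power Analysis: "with two-tailed alpha = .05 for any comparison between message arms". Analysis Notes deals with intent-to-treat, one patient per phone number, the choice of OLS and robust standard errors, but not with multiplicity. Analyses 2 and 3 are labelled exploratory.

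The Brief Summary adds a further aim: "The study will also test which of several message versions is most effective". On timing, Project Status says: "We have not yet extracted outcome data as of this writing".

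**The concern.** The hypothesis is a union: one success among four comparisons is enough to support it. The error rate that matters for such a claim is the probability of at least one false success, not the error rate of each test. If every arm is tested at .05, the first is well above the second, and nothing in the SAP limits it.

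The problem is not confined to the case where messaging does nothing. If one version works and the others do not, unadjusted tests can still credit an ineffective version. The authors want to say something about individual versions, so arm-level claims are to be expected. Without a written rule, the choice between adjusted and unadjusted p-values could also be made after the results are known.

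**Working it through.** **Inputs, all from Power Analysis unless noted**
- Arms: five (one passive control, four message arms; Methods), 10,000 patients each.
- Control rate 4.1%; target rate 4.9%, a difference of 0.8 points.
- Two-tailed alpha .05 per comparison, critical value 1.96. Applying it to each coefficient in Analysis 1 is an inference.
- Final enrollment 50,785 (Project Status), or 50,785/5 = 10,157 per arm if equal.

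**1. The plan's own power figure**

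SE = √[(.041×.959 + .049×.951)/10,000] = √(.085918/10,000) = .00293.
Power = Φ(.008/.00293 − 1.96) = Φ(2.729 − 1.960) = Φ(0.769) = 77.9%.

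The difference detectable with exactly 80% power is 0.82 points, which rounds to the stated 0.8. The plan's figure therefore reproduces at its own rounding, on the basis of a single, uncorrected two-sided .05 comparison. This supports .05 per arm as the intended reading.

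**2. Error rate when no arm works**

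Equal arms sharing one control give a correlation of ρ = 0.5 between any two of the four z-statistics. For critical value c:

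- P(at least one false increase) = 1 − ∫ Φ[(c + √ρ·x)/√(1−ρ)]⁴ φ(x) dx
- P(at least one rejection in either direction) = 1 − ∫ {Φ[(c + √ρ·x)/√(1−ρ)] − Φ[(−c + √ρ·x)/√(1−ρ)]}⁴ φ(x) dx

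| Rule | False increase | Either direction |
|---|---|---|
| One test at .05 | 2.5% | 5.0% |
| Four tests at .05 each (c = 1.96) | 7.8% | 15.6% |
| Dunnett (c = 2.442, per-test alpha .0146) | 2.5% | 5.0% |
| Holm | 2.2% | 4.3% |

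A simulation of 400,000 five-arm binomial trials at 4.1%, with unpooled standard errors, gave 7.8% and 15.6% for the unadjusted rule. If the four contrasts were independent, the rates would be 1 − .975⁴ = 9.6% and 1 − .95⁴ = 18.5%; the shared control lowers them somewhat. With unequal allocation, message-to-control ratios from 0.25 to 4 move the false-increase rate from 9.1% to 5.7%, always above 2.5%.

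**3. Error rate when some arms work (+0.8 points each; 400,000 simulated trials per scenario)**

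| Working arms | False claim in a non-working arm, unadjusted | With Dunnett |
|---|---|---|
| 1 | 6.2% | 1.9% |
| 2 | 4.5% | 1.4% |
| 3 | 2.5% | 0.7% |

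**4. Power after adjustment**

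Single-arm power with Dunnett = Φ(2.729 − 2.442) = Φ(0.287) = 61%. With Holm it is 59%, 61%, 64% and 68% when one, two, three or four arms work. The difference detectable with 80% power rises from 0.82 to 0.97 points under Dunnett.

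| Working arms | At least one found, unadjusted | With Dunnett |
|---|---|---|
| 1 | 78% | 61% |
| 2 | 90% | 77% |
| 3 | 94% | 84% |
| 4 | 96% | 88% |

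At 10,157 per arm, single-arm power is 78.5% unadjusted and 62% with Dunnett. The analysed number will be smaller once one patient per phone number is chosen, by an amount the SAP does not give.

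**The case against.** The strongest reply is that 7.8% depends on a rule the SAP never states. Analysis 1 gives no alpha, and one hypothesis attached to one categorical predictor could be read as a joint test of that predictor. If a four-degree-of-freedom test at .05 had to be passed first, the false-increase rate with no working arm would be about 2.0%. It is right that the figure is conditional. But the SAP names no such gate, and a joint test has no direction, so alone it cannot show an increase. Even as a gate it leaves a 5.9% chance of a false claim for another arm when one arm works, close to the ungated 6.2%.

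It can also be said that the SAP never promises 2.5%; its stated level is two-tailed .05. That is true. The pair 7.8% and 2.5% follows the directional wording of the hypothesis, and 15.6% against 5% is the two-sided equivalent. The inflation is about threefold either way.

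The aim of finding the most effective version concerns contrasts between message arms, which adjustment against passive control neither answers nor protects. This stands: that sentence shows only that individual versions are of interest.

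Finally, all message arms share the same core prompt, so a pooled or joint gate followed by Holm is also a valid way to control the familywise error. This stands as a matter of principle. If all four arms work, the pooled contrast has 94% power, against 88% for at least one arm under Dunnett. With one, two or three working arms it has 15%, 44% and 76%, against 61%, 77% and 84%.

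**Conclusion.** The concern holds. The plan makes one confirmatory claim over four comparisons and states nothing that controls its error. Read with the only alpha given, the chance of falsely claiming that some arm increases vaccination is 7.8% instead of 2.5%, or 15.6% instead of 5% in either direction, when no arm works. It is 6.2% for the remaining three arms when one works.

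These figures assume equal arms of 10,000, a 4.1% control rate and each coefficient tested at two-tailed .05. The absence of a decision rule is plain from the text; the .05 per arm is inferred from Power Analysis. The arm estimates themselves remain valid. What lacks a defined error rate is the confirmatory conclusion, so this should be fixed but does not invalidate the trial.

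**What to change.** State in Analysis 1 that the four comparisons with passive control will use two-sided p-values adjusted by Dunnett's method (critical |z| about 2.44) or by Holm's, and name one of the two. Take them from the same OLS model with robust standard errors, and rest any claim that an arm increases vaccination on the adjusted p-value.

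A pooled contrast of all messages against passive control is best kept as a supplementary estimate. As a gate it loses much power if only one or two arms work. As an extra .05 test beside ungated Dunnett tests, it raises the chance of any false rejection to 7.1% when no arm works.

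The change takes one or two sentences and no new data. The SAP is dated 7/9/2025 and plans EHR extraction that same month, so the time for a clean prespecification is short. The amendment should be dated and should state whether outcome data had been extracted.

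The price is power. For one arm at 4.1% versus 4.9% it falls from 78% to 61% with Dunnett, or to 59–68% with Holm depending on how many arms work. The power statement should be revised to match: with Dunnett, 80% power corresponds to a difference of about 0.97 points at 10,000 per arm.

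### The confirmatory regression uses arm indicators alone and leaves unused baseline variables that the trial already holds: a small, optional gain in precision, not an error

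*SAP*

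**What the plan says.** SAP, Planned Analyses, Question 1, Analysis 1 (Confirmatory): "We will run an OLS regression including a categorical predictor variable coding for each individual arm, with passive control as the baseline". No other predictor is listed. The Analysis Notes add heteroskedasticity-robust standard errors for all analyses and keep one patient per phone number in the primary analysis.

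The baseline variables appear elsewhere in the SAP:

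- **Age, sex, race and insurance group.** The Analysis Notes reserve these for exploratory work on heterogeneity, as "demographic covariates such as age, sex, race, whether the patients were GHP members".
- **Insurance group.** It also enters the exploratory cost-by-insurance interaction and the rule for choosing one patient per phone number.
- **Enrolment date.** It is known for every patient and differs by insurance group: "Enrollment began with patients who have a GHP membership, followed five weeks later by enrollment for those without GHP" (Past Project Status Notes). It also serves to pick the first patient enrolled on a shared phone number. It is not a covariate in any model.

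The SAP describes randomisation by phone number and mentions no stratification factor. At its date (7/9/2025), outcome data had not been extracted.

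**The concern.** The SAP itself gives reasons to expect some of these variables to predict recorded vaccination:

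- Claims supplement the EHR only for GHP members, so a vaccination outside Geisinger can be captured in one insurance group and not in the other.
- The two insurance groups were launched five weeks apart.
- During the September to December 2024 flu campaign, patients entered the study if the EHR already showed a flu vaccine that season. They may be readier to accept vaccines than patients enrolled in other months.

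A model without these variables leaves the variation they explain in the residual and does not correct chance imbalance in insurance mix or season between arms. At stake is the width of the confirmatory intervals. Validity is not in question. Enrolment has closed and the messaging platform has been decommissioned, so precision can no longer be bought with more patients.

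**Working it through.** **Inputs from the SAP (Power Analysis).** Control rate 4.1%, alternative 4.9%, difference 0.008. Sample: "With 50,000 patients, and 10,000 patients per arm, we have 80% power". Test: "with two-tailed alpha = .05 for any comparison between message arms".

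**Input not in the SAP (assumption).** R-squared, the share of outcome variance explained by the covariates. I take 0.3% to 2% and show larger values for reference.

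**Step 1. Reproduce the stated power.**
- Mean rate = (0.041 + 0.049)/2 = 0.045.
- SE of the difference = sqrt(2 × 0.045 × 0.955 / 10,000) = 0.00293.
- z = 0.008 / 0.00293 = 2.729, and 2.729 − 1.960 = 0.769. Power = Φ(0.769) = 77.9%.
- The unpooled variance also gives 77.9%, and the arcsine method 78.0%.
- The difference detectable with 80% power is 0.822 points, which rounds to the stated 0.8.
- A residual variance pooled over all five arms, four of them at 4.1%, gives 80.0%. Because the SAP plans robust standard errors, the two-arm figure of 77.9% is the relevant starting point.

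**Step 2. What R-squared is plausible?** For a two-group covariate, R-squared = share × (1 − share) × d² / [p(1 − p)], with p = 0.041 and p(1 − p) = 0.041 × 0.959 = 0.0393.
- Two equal groups at 3.0% and 5.2% (assumed): 0.25 × 0.022² / 0.0393 = 0.3%.
- Two equal groups at 2.0% and 6.2% (assumed): 0.25 × 0.042² / 0.0393 = 1.1%.
- For a combined baseline risk score with mean risk 4.1%, simulation gives R-squared of about 0.7% at an AUC of 0.61, 1.6% at 0.66, 3.0% at 0.71 and 5.0% at 0.755.

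With so rare an outcome, even a useful predictor explains little variance. Hence the working range of 0.3% to 2%.

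**Step 3. Effect of adjustment.** SE ratio = sqrt(1 − R²); equivalent n per arm = 10,000/(1 − R²); power = Φ(2.729/sqrt(1 − R²) − 1.960).

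| R-squared (assumed) | SE reduction | Equivalent n per arm | Power, 4.1% vs 4.9% |
|---|---|---|---|
| 0 | 0 | 10,000 | 77.9% |
| 0.3% | 0.15% | 10,030 | 78.0% |
| 1% | 0.5% | 10,101 | 78.3% |
| 2% | 1.0% | 10,204 | 78.7% |

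In the working range the gain equals about 30 to 204 patients per arm, or 0.1 to 0.8 points of power. For reference, an R-squared of 3% gives 79.1%.

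**The case against.** The strongest case against raising this is that the plan contains no mistake. Arm-only OLS with robust standard errors is unbiased, the SAP states no stratification that the model would have to reflect, and the power statement does not rely on adjustment. The present model is also fully determined, whereas added covariates bring choices about coding, cut-points and missing values into the only confirmatory test. The claims argument is weak for the primary outcome, since the SAP expects most vaccinations to be in the EHR. The gain is also small beside ordinary variation in sample size: at 50,785/5 = 10,157 per arm, unadjusted power is already 78.5%, although that count precedes the reduction to one patient per phone number.

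Most of this stands. It fixes the size of the point and rules out calling it an error. It does not remove the point: the data are in hand, the estimand is unchanged, and at about 10,000 per arm adjustment cannot materially harm precision. The worry about discretion is met by a short covariate list with stated coding.

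A reader might infer two stronger things. One is that the missing 2 points of power (77.9% against 80%) can be recovered by adjustment. That needs an R-squared of about 5%, hence a baseline score with an AUC of about 0.755, and nothing in the documents supports it. The other is that adjustment is free. It is not quite, because coding and missing-value rules must be fixed beforehand.

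**Conclusion.** The point holds as an optional refinement. The confirmatory analysis is valid as written but passes up a small gain in precision from variables the trial already has. Under an assumed R-squared of 0.3% to 2%, standard errors shrink by about 0.15% to 1%, and power for the planned difference moves from 77.9% to about 78.0% to 78.7%. The result rests on that assumption, on 10,000 analysed patients per arm and on the SAP's two rates. The SAP gives neither the true R-squared nor the number analysed after selecting one patient per phone number. That the detectable difference is 0.82 points, rounded to 0.8, is no evidence that the model is deficient.

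**What to change.** Before outcome extraction, amend Analysis 1 to specify OLS of the primary outcome on the four arm indicators (passive control as reference) plus:

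- GHP or non-GHP group, as grouped for the study;
- enrolment period, as indicators for calendar month;
- age, linear;
- sex.

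Keep the robust standard errors, and report the unadjusted model as a sensitivity analysis. Full arm-by-covariate interactions are not needed.

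The cost is a few sentences stating the coding and a simple missing-value rule, namely a missing-indicator category. Insurance group and enrolment date should be complete, because the study used both to run enrolment. No new data are needed.

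Timing matters. The SAP schedules EHR extraction for July 2025, the month of its own date. If outcomes have already been extracted, the unadjusted model should stay confirmatory and the adjusted one be added only as a labelled sensitivity analysis, since a later switch would be open to the charge of selection.

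### Two optional robustness checks need a tighter rule: the delivered-only check does not fit passive control, and the all-patients check names no clustering on phone number (minor; primary analysis unaffected)

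*SAP*

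**What the plan says.** The SAP's Analysis Notes state: "The primary analyses described above will be intent-to-treat". The same sentence continues: "we may run follow-up robustness checks limited to patients for whom messages were delivered successfully according to messaging data". The check is therefore optional and is attached to the primary analyses.

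The confirmatory one is Analysis 1 under Planned Analyses: "We will run an OLS regression including a categorical predictor variable coding for each individual arm, with passive control as the baseline". The Methods section lists that baseline as "Passive control: No message". Analyses 2 and 3 are exploratory and are expressly confined to patients in a message arm. Neither Analysis 1 nor the delivered-only check carries such a limit.

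On phone numbers, Methods says that randomisation was at the level of the number, so people sharing one were sent the same version. The Analysis Notes give this as the reason for keeping one patient per number in the primary analysis, and then allow an optional check with everyone included. They specify heteroskedasticity-robust standard errors for every analysis and do not mention clustering.

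**The concern.** Readers take a robustness check as support for the main result, so it should not be able to move for reasons unrelated to treatment.

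**(a) Delivered-only check.** A delivery filter can act only on patients who were sent something. Applied to Analysis 1, it trims the message arms by an event after randomisation and leaves the control arm whole. Patients whose messages fail may differ from the rest in how often they vaccinate. If so, the two sides no longer compare like with like, and a gap can appear or shrink with no effect of messaging.

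**(b) All-patients check.** Patients who share a number were assigned together. Heteroskedasticity-robust errors do not by themselves allow for correlation within a number, so intervals could be slightly too narrow.

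**Working it through.** **Scale for comparison.** The Power Analysis section gives 4.1% against 4.9%, 10,000 per arm, two-sided alpha 0.05 and 80% power. Unpooled SE = √[(0.041×0.959 + 0.049×0.951)/10,000] = 0.293 points. Power = Φ(0.8/0.293 − 1.96) = 77.9%. The detectable difference at exactly 80% is 0.82 points, which rounds to the stated 0.8. The point does not depend on this figure; it only supplies a yardstick.

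**(a) Delivered message patients against all controls, no true effect.** From the SAP: 4.1% and 10,000 per arm. Assumed, because the SAP gives neither: the undelivered share u, and k, the vaccination rate in undelivered patients divided by that in delivered patients.

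- Rate in delivered patients: d = 0.041/(1 − u + uk)
- Spurious difference: d − 0.041
- z = (d − 0.041)/√[d(1 − d)/(10,000(1 − u)) + 0.041×0.959/10,000], with two-sided rejection at 1.96

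| u | k | d | Spurious difference (points) | Chance of p < 0.05 |
|---|---|---|---|---|
| 2% | 0.5 | 0.041/0.990 = 4.141% | +0.04 | 5.2% |
| 5% | 0.5 | 0.041/0.975 = 4.205% | +0.11 | 6.6% |
| 2% or 5% | 1 | 4.100% | 0 | 5.0% |
| 2% | 1.25 | 0.041/1.005 = 4.080% | −0.02 | 5.1% |
| 5% | 1.25 | 0.041/1.0125 = 4.049% | −0.05 | 5.4% |

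The sign follows k, and the SAP has no information on k.

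**(b) All patients, clustering ignored.** Assumed: a share s of patients share a number in pairs, with within-pair correlation ρ. The SAP gives neither.

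- Design effect: DE = 1 + sρ
- SE shortfall: 1 − 1/√DE
- Type I error: 2[1 − Φ(1.96/√DE)]

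At ρ = 0.1:

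- s = 5%: DE = 1.005, SE 0.25% too small, type I error 5.1%
- s = 30%: DE = 1.03, SE 1.5% too small, type I error 5.3%

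If the 50,785 patients in Project Status count everyone enrolled, the check adds back 50,785 × s/2, which is about 1,270 patients at 5% and 7,618 at 30%.

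**The case against.** Both checks are optional. The SAP already uses the main safeguards: intent-to-treat for the primary analyses, and one patient per number because of the unit of randomisation. With one patient per number, heteroskedasticity-robust errors are adequate. All of that stands, and it is why the point is minor.

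Several stronger readings are tempting, but the document does not support them:

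- **The check empties the control arm, so Analysis 1 cannot be run.** This follows only from a literal reading. No analyst would delete the controls and then report a contrast with them. The realistic problem is selection on one side.
- **The SAP rules out clustering.** It does not. Cluster-robust errors are also heteroskedasticity-robust. The text does not name them, so an analyst following it as written could leave them out.
- **The distortion is large, or favours messaging.** Bigger figures can be produced. With 10% undelivered and k = 0.5, the shift is +0.22 points and the chance of false significance 11.5%. With 30% sharing and ρ = 0.5, type I error is 6.8%. Nothing in the SAP supports these inputs. At a 4.1% rate, ρ = 0.5 means that if one patient is vaccinated on the appointment date, the other has a 0.041 + 0.5×0.959 = 52% chance, which is implausible for an outcome tied to each patient's own appointment.
- **Clustering is the only issue in the all-patients check, and its point estimate is sound.** This is not established either. The Analysis Notes foresee patients on one number enrolling on different days, so a later patient may enter after messages went to that number. The SAP does not show that such enrolment is independent of arm.

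The SAP also does not say what counts as delivered when one condition has "Two messages: Messages 3 days and 1 day before the appointment" and the other "Three messages: Messages 3 days, 2 days, and 1 day before the appointment". That is a missing detail in an optional check rather than an error.

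**Conclusion.** The point holds as a minor one, confined to two optional checks. The primary estimate and the confirmatory decision do not change.

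(a) Used on Analysis 1, the delivered-only check compares a post-randomisation subset of message patients with all controls. It can shift with no true effect, by an amount and in a direction that the SAP cannot establish. At 2–5% undelivered, the shift is +0.04 to +0.11 points if k = 0.5, zero if k = 1, and −0.02 to −0.05 if k = 1.25. The design difference is 0.8 points. Analyses 2 and 3 keep their reference group, but a delivered-only version would still condition on a status that arises after randomisation.

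(b) Followed as written, the stated standard errors ignore correlation within a number in the all-patients check. The size is unknown and probably small: about 5.1–5.3% type I error at ρ = 0.1 with 5–30% sharing in pairs, and higher only under stronger assumptions.

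**What to change.** Add to the Analysis Notes:

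1. Every contrast with passive control keeps all randomised patients in the analysis set. Delivered-only checks are limited to contrasts among message arms and are labelled as conditioning on a post-randomisation status.
2. If an effect of delivery against passive control is wanted, use assigned arm as the instrument for delivery, on the assumption that assignment acts only through delivery. Label the result a rescaling of the intent-to-treat effect, not independent confirmation. For example, 0.80 points becomes 0.80/0.98 = 0.82 at 2% undelivered and 0.80/0.95 = 0.84 at 5%.
3. Standard errors are cluster-robust on phone number in any analysis with more than one patient per number.

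A one-line definition of delivered would help. The report of the all-patients check should also note that some patients may have enrolled after messages had gone to their number.

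The cost is a few sentences and slightly wider intervals in one optional check. The instrumental estimate adds little beyond intent-to-treat and can be left out. Project Status says that outcome data had not been extracted at the time of writing, so the change can be made without knowledge of results if that is still the case.
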